Title: RCT of Mindfulness-Enhanced Pivotal Response Group Treatment on Parenting Stress

NCT# not yet assigned

Document date: 6/1/2023

Study Protocol and Statistical Analysis Plan

Participants

A total of 15 caregivers and children will be randomly assigned to mPRT or pPRT groups. Inclusion criteria for children includes the following: 1) current or suspected ASD diagnosis, verified by ADOS-2, brief clinical interview, and expert clinical opinion using DSM-5 criteria; 2) demonstrates ability to make meaningful vocalizations; 3) no active medical problems (e.g., unstable seizure disorder). Inclusion criteria for participating caregiver includes the following: 1) no severe mental health problems (e.g., suicidal intent; psychosis); 2) willingness to record weekly videos and share in a group setting.

Participants will be recruited from Southwest Virginia via multiple methods (e.g., university and non-university clinics, registries, local ASD support groups, parent resource centers, local service agencies or schools). A two-stage eligibility process will be used. First, caregivers who expressed interest in the study will complete a phone interview to screen for study eligibility. Caregiver and child dyads who appeared to meet eligibility criteria and who were still interested in the study based on the phone screen will then be scheduled for a two-session assessment appointment to confirm diagnosis and eligibility.

Procedure

All interested families will complete a phone screen to determine initial eligibility criteria. Those who qualify will be invited to participate in two screening visits at the VT Autism Clinic (approximately 3.5 hours total). Parents will be provided with the option to complete all components in one day or two days. During these visits, a clinician will administer the Autism Diagnostic Observation Schedule- 2nd Edition (ADOS-2) to the child and the participating

caregiver to confirm the child's diagnosis of ASD, as well as the Mullen Scales of Early Learning (MSEL), a measure of cognitive ability.

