Randomization. Eligible families will be randomly assigned to either the mindfulness enhanced mPRT or to pPRT as the control condition. The Randomization Module in REDCap will be completed by a research assistant, blind to the clinician completing the pre-treatment assessment. Groups will be matched on gender of caregiver to control for gender differences previously reported in parenting stress literature (Davis and Carter, 2008). Both caregivers are permitted to attend groups; however, one caregiver must identify as the primary reporter (i.e., individual who completes all self- and parent-report questionnaires, attends sessions regularly, and participates in all home videos).

If challenges with recruitment emerge, randomization rules may be adjusted. In this instance, once the period of recruitment has commenced and 3 or more families have completed the pre-assessment condition, a random number generator will be used to determine the group for the individuals.

Treatment (Appendix A). All families will receive the same dose of PRT parent training delivered in a previously studied package (e.g., Hardan et al., 2014) that includes 16 hours of group sessions and 4 hours of individual sessions, delivered over a 12-week timeframe. The format for teaching PRT techniques and abilities will be replicated from Hardan et al. (2014), who adapted the material from the manual, “How to Teach Pivotal Behaviors to Children with Autism” (Koegel et al., 1989) and has been previously implemented in a feasibility study by the current researchers.

Additionally, all parents will receive 6 hours total of group supplemental treatment that specifically targeted parenting stress either by mindfulness-based techniques or by psychoeducation (depending on random assignment). Materials from the psychoeducation group include didactic training on a variety of topics focusing on the parent, child and family outcomes. For example, literature on general parenting stress as well as parenting stress in parents of children with ASD was one topic presented in an informational manner, without providing instruction regarding specific skills training.

The mindfulness-enhanced treatment, on the other hand, provides specific skills as well as didactic information about applying mindfulness to the parenting role. Components from ACT as well as Mindful Parenting will be incorporated into the weekly sessions in a manner that applied the mindfulness skills to the newly learned PRT skills.

Measures

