Group differences. Pending anticipated non-normal distributions of the small samples, Mann-Whitney U tests will be used to make baseline comparisons to compare independent samples (i.e., completers versus non-completers; mPRT versus pPRT). G*Power3 (Faul, Erdfelder, Lang, & Buchner, 2007) power analyses will be completed to evaluate the size of effect one can be expected to obtain given the obtained sample size, and $\alpha = .05$. A sample size of 95 will be necessary to detect a large effect ($r = .5$). Group comparisons will also be made at post-treatment to analyze differences in parent fidelity of PRT techniques and treatment satisfaction. To calculate effect size, the following formula will be ($r = Z/\sqrt{N}$). The

interpretation of r values are as follows: .5 = large effect, .3 = medium effect, .1 = small effect (Coolican, 2009; Fritz, Morris, & Richler, 2012).

In addition, to test within-group changes, non-parametric Wilcoxon Signed Rank Test (equivalent to a dependent t -test) will be used to compare baseline and endpoint/follow-up scores for each group across variables of interest. A sample size of 27 will be necessary to detect a large effect ($r = .5$) and 648 for a small effect ($r = .1$). Due to low power, effect sizes will also be calculated when determining change as a result of treatment.

Single-Subject Analyses. In addition to group change over time, individual level change will be calculated for parenting stress, parent mindfulness, and parent positive feelings toward child using Reliable Change Index (RCI; Jacobson & Truax, 1991). RCIs will be calculated to determine the magnitude of change needed to show meaningful change above and beyond standard error. RCI calculations will be completed by dividing the difference of scores between two timepoints (i.e., either pre-treatment and post-treatment or pre-treatment and follow-up), divided by the standard difference, which includes test-retest reliability and standard deviation of the original measure. RCI values above 1.96 are suggested to infer statistically significant and meaningful change. The test-retest reliabilities and standard deviations used to compute the S_{diff} score will be obtained from the literature. If test-retest reliability was not previously reported in literature, then Cronbach's alpha was used (from the literature).

Table 1
Assessment Schedule

Construct/ Measure	Pre-Tx	Mid	Weekly	Post-Tx	Follow-up
Sample Characterization					
ADOS-2	X				

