Appendix A

Session Fidelity Rating Form

Date of session:

Length of session (timed): _____ min

Treatment visit #:

Randomization group: mPRT

pPRT

Therapists (list all names):

Number of parents present:

1. How many of the stated objectives for the session did the therapist(s) complete?

of objectives met/ # of objectives stated for this session = _____ / _____

2. Was homework assigned from the previous session?

0 = NO

1 = YES

2a. IF YES → Did the therapist(s) review practice/homework assigned in previous session (even if homework was not completed)?

0 = NO

1 = YES

3. Did the therapist(s) explain or preview the session agenda at start of session?

0 = NO

1 = YES

4. How would you describe the therapeutic relationship during the session?

1 = Very poor (e.g., no responding to questions or materials that are posed)

2 = Less than ideal (e.g., partial responding to questions that are posed)

3 = Average (e.g. responds to questions that are posed, seem to understand concepts covered)

4 = Good (e.g., parent asks at least one question or provides elaboration or example, brings up new information or content)

5. Please rate how engaged the caregivers were in the group.

1 = Unengaged

2 = Minimally engaged

3 = Moderately engaged

4 = Actively engaged

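### Families share arm-specific treatment groups but are tested as independent, so the false-positive rate can exceed .05 and a group difference can pass for an arm effect

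*Combined protocol and SAP*

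**What the plan says.** Participants sets the size: "A total of 15 caregivers and children will be randomly assigned to mPRT or pPRT groups". Randomization makes the family the unit: "Eligible families will be randomly assigned to either the mindfulness enhanced mPRT or to pPRT as the control condition".

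Treatment is mostly shared. The PRT package "includes 16 hours of group sessions and 4 hours of individual sessions, delivered over a 12-week timeframe", and "all parents will receive 6 hours total of group supplemental treatment" on top of it, with content that depends on the assigned arm. The treatment outline agrees: 11 two-hour group sessions and four one-hour individual sessions. The Session Fidelity Rating Form records one randomization group per session and has a line for therapists ("Therapists (list all names").

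Under Group differences, the Statistical Analysis Plan names Mann-Whitney U for independent samples and Wilcoxon signed rank within each arm. It adds: "Group comparisons will also be made at post-treatment to analyze differences in parent fidelity of PRT techniques and treatment satisfaction". It contains no group or therapist term, ICC, design effect or caveat. The number of groups per arm, their size and the assignment of therapists to arms are not given.

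**The concern.** Parents in one group hear the same sessions, watch each other's home videos and get feedback together. A strong or weak group can move all its members the same way. Because each group belongs to one arm, that shared shift enters the arm difference directly, and a test that counts every family as separate information understates the uncertainty.

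The two outcomes named for post-treatment arm comparison, parent PRT fidelity and satisfaction, are ones that group climate and leadership can plausibly affect. At stake is whether a significant difference gets reported as an effect of mindfulness when it reflects one good group. The within-arm Wilcoxon tests have the same weakness: a shift common to one group reads as treatment change.

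**Working it through.** **Inputs from the documents.** 15 families; 16 h group PRT, 6 h group supplement and 4 h individual; alpha = .05.

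**Assumptions.** An 8 v 7 split; one, two or three groups per arm; ICC 0 to .20; normal outcomes with a random group effect; no true arm effect; two-sided tests.

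**1. Share of treatment given in groups.** 16 + 6 = 22 group hours; 22 + 4 = 26 in total; 22/26 = 85%. The outline gives the same: 11 x 2 = 22 and 4 x 1 = 4.

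**2. Baseline under independence.** The exact 8 v 7 Mann-Whitney test rejects if U <= 10 or U >= 46, with a true size of .040. With no clustering, the plan's .05 is respected.

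**3. Size of the clustering effect by hand, one group per arm.** Set the total variance to 1. The variance of the difference in arm means is (1/8 + 1/7)(1 - ICC) + 2 x ICC.
- ICC 0: .268.
- ICC .10: .268 x .90 + .20 = .441, a ratio of 1.65.

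The design effect 1 + (m - 1) x ICC with m = 7.5 agrees: 1 + 6.5 x .10 = 1.65. A normal test with a 1.96 cut-off then effectively cuts at 1.96/sqrt(1.65) = 1.53, a two-sided error of about .13. At ICC .05 and .20 the design effects are 1.325 and 2.30, and the errors about .09 and .20.

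**4. Simulated false-positive rate of the exact Mann-Whitney test (200,000 null trials per cell).**

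| Groups per arm | ICC 0 | .05 | .10 | .20 | Passes .05 at ICC of about |
|---|---|---|---|---|---|
| 1 (8 v 7) | .040 | .07 | .11 | .19 | .016 |
| 2 (4+4 v 4+3) | .040 | .05 | .07 | .10 | .04 |
| 3 | .040 | .047 | .056 | .073 | .07 |

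The normal-approximation version, which supplies the Z in the plan's r = Z/sqrt(N), starts at .054. With one group per arm it gives about .09 at ICC .05 and .14 at ICC .10.

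**5. Within-arm Wilcoxon, 8 families in one group.** .039 at ICC 0, then .071, .106 and .181 at ICC .05, .10 and .20.

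**6. Therapist.** If one therapist serves both arms equally, that therapist's main effect cancels and the simulated error stays at .040.

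**7. Does a sensitivity p-value behave?** The design effect is a variance factor, so Z must be divided by its square root. With the true ICC and ICC .05 / .10 / .20, that gives about .04 / .04 / .03 with one group per arm, and .035 to .048 with two or three. Dividing by the full design effect would give .015 / .003 / .000 with one group per arm. At ICC .20, complete separation of the arms has Z = 28/8.64 = 3.24. Divided by 2.3 that is 1.41 (p about .16), so .05 could never be reached. Divided by sqrt(2.3) = 1.52 it is 2.14 (p about .03).

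**The case against.** The strongest reply is that the inflation is conditional. A reader might infer that the error rate does exceed .05. The documents do not support that: they give no ICC and no group count, and the exact test starts at .040. The fallback rule in Randomization acts once three or more families have completed pre-assessment, so several small cohorts are possible. With three groups per arm and ICC .05 the rate is .047. This stands, and the point is therefore that the rate can exceed .05. Alpha = .05 is also given as an input to the power calculation, not expressly as the level of these tests.

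A reader might also infer that therapist is confounded with arm. Nothing says that therapists differ between arms; the rating form only lists names by session. Nor can cluster randomization be inferred from the fallback wording, "a random number generator will be used to determine the group for the individuals", which leaves open whether families are drawn singly or together. Finally, the sentence on post-treatment comparisons names fidelity and satisfaction; it should not be read as planning an arm comparison of parenting stress.

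The plan has partial safeguards: equal PRT dose in both arms, rated therapist fidelity and group engagement in 5 to 6 of 11 sessions, an admission of low power, effect sizes and individual change indices. They mean that conclusions need not rest on p-values alone. They do not remove the problem, because the ratings enter no outcome analysis and an effect size computed from Z carries the same group shift.

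**Conclusion.** The concern holds in conditional form. Group delivery, nesting of groups in arm and the absence of any allowance for it are all documented. The size rests on assumed values: over ICC .05 to .20 the exact Mann-Whitney error is about .07 to .19, .05 to .10 or .05 to .07 with one, two or three groups per arm, given an 8 v 7 split and normal outcomes.

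The limit on interpretation is firmer than the error rate. With one group per arm, no analysis can separate group from arm, whatever the ICC. The change is worth making because it alters what the trial may claim, and it needs no change to treatment or recruitment.

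**What to change.** - Record treatment-group ID and lead-therapist ID for every family in REDCap. State in the plan the number and size of groups per arm and whether therapists serve one arm or both.
- Beside each post-treatment arm comparison (parent PRT fidelity, satisfaction), report a sensitivity p-value with the Mann-Whitney Z divided by the square root of 1 + (m - 1) x ICC, for ICC .05, .10 and .20, where m is the realised group size. Show results by treatment group.
- State that unadjusted p-values, including those from the within-arm Wilcoxon tests, assume no group effect.
- State that if there is only one group per arm, a difference will be described as one between those two groups and not as an effect of mindfulness.

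A rank test on group-level results is not a substitute here. Its smallest two-sided p is .33 with 2 v 2 groups and .10 with 3 v 3; it first passes below .05, at .029, with 4 v 4.

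The cost is two data fields, a short extra table and less favourable p-values. No additional families or staff are needed.

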Therapist fidelity of treatment implementation (Appendix B). A licensed clinical psychologist trained in PRT will view 5-6 group sessions out of the 11 total group sessions (i.e., 45 to 54% of the total group sessions) to assess for therapist fidelity of treatment implementation. The videos will be randomly assigned for viewing before all groups commenced and the

randomization was blind to treatment providers. Fidelity will be assessed on completion of specific session goals, therapeutic relationship, and level of group engagement.

Child utterances (Appendix C). The level or amount of child utterances during in-laboratory semi-structured tasks and in-home naturalistic environments will be coded by trained undergraduate research assistants using *Noldus The Observer XT* (version 12.0 software, Noldus Information Technology, Leesburg, VA, USA). All videos will be double coded by undergraduate research assistants who were blinded to treatment condition and treatment phase. Three total coders will complete double coding for all videos. Interrater reliability will be assessed by Kappa and Rho, due to the complexity of the coding system. All research assistants will attend group training in behavioral coding and child utterances and will attain above 80% fidelity with sample videos coded by a master's level clinician. As modeled in Hardan et al. (2014), child utterances consist of the following: unintelligible (e.g., sound produced by child that does not appear to demonstrate an attempt at a meaningful utterance; "lalalala"), imitative (e.g., parent models the word and encourages child to imitate exact word), verbally prompted (e.g., parent asks a question with open-ended response), nonverbally prompted (e.g., parent presents an opportunity for language by holding an object in sight and out of reach) and spontaneous (i.e., not prompted by the parent). To reduce variability, the amount of child utterances was expected to increase in both groups from pre SLO to post and follow-up SLO. Amount of child utterances were examined to determine effectiveness of treatment across groups.

In the current study, differences in child utterances will be calculated using changes in SLO and weekly videos will also be used to estimate changes in average utterances from weeks 1 and 2 to weeks 9 and 10. Because frequency/total counts were used for analyses, weekly videos will be excluded from analyses if they were less than 9 minutes in length.

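### Child utterance change is tested only within each arm, although both arms receive the same PRT; one prespecified test on all families would roughly double power at moderate to large effects

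*Combined protocol and SAP*

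**What the plan says.** **Sample.** Participants: "A total of 15 caregivers and children will be randomly assigned to mPRT or pPRT groups". No allocation ratio is given, and the Randomization paragraph allows the rules to be adjusted if recruitment is difficult.

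**Treatment.** Procedure, Treatment: "All families will receive the same dose of PRT parent training delivered in a previously studied package". The arms differ only in the supplement: "all parents will receive 6 hours total of group supplemental treatment", either mindfulness-based or psychoeducational.

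**The utterance question.** Measures, Child utterances: "the amount of child utterances was expected to increase in both groups from pre SLO to post and follow-up SLO", followed by "Amount of child utterances were examined to determine effectiveness of treatment across groups".

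**The test.** Statistical Analysis Plan, Group differences: the Wilcoxon signed-rank test "will be used to compare baseline and endpoint/follow-up scores for each group across variables of interest". The same section says that 27 are needed for a large effect (.5) and 648 for a small one (.1), admits low power and adds effect sizes. Its Mann-Whitney comparisons are named for baseline and, after treatment, for parent fidelity and satisfaction. None is named for utterances after baseline. The single-subject analyses cover parenting stress, mindfulness and positive feelings, not utterances.

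**The concern.** Utterances are the outcome most directly tied to the treatment that both arms share. Whether children talk more after PRT is a question that all 15 families can answer together, but the plan answers it twice, on about 7 and about 8 families.

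Two things are at stake. First, each test has much less power than one test on everyone. Second, the two per-arm p-values would be the only inferential information on utterances by arm. If one falls below .05 and the other does not, readers may conclude that one supplement improved the response to PRT. The plan has no rule against that reading and no direct comparison of utterance change to check it.

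**Working it through.** **1. The plan's own figures.** I read .5 and .1 as the standardised mean change, dz = mean change / SD of change. I took one-sided alpha .05, 80% power (the target is not stated) and paired-t power with n scaled by the Wilcoxon efficiency 3/π. This gives 28 and 649, against the stated 27 and 648. At 27 and 648 the computed power is 79.5% and 80.0%, so the figures are reproduced within rounding. Two-sided, the same method gives 35 and 824. The SAP labels the effects r = Z/√N. On that reading (z₁₋α + z₀.₈)² / r² gives 24.7 and 618.3 one-sided, or 31.4 and 784.9 two-sided, which fits less well. The sidedness of the planned tests therefore stays open, and both are shown below.

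**2. Inputs for the comparison.**
- From the documents: 15 families, alpha .05, the same PRT in both arms, a signed-rank test within each arm.
- Assumed: arms of 7 and 8, no dropout, normal change scores, the same true dz in both arms, an exact test, and dz from .5 to 1.5. The documents give no SD or effect size for utterances.

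**3. Exact two-sided rejection rules.** Under no change, all 2ⁿ sign patterns are equally likely.
- n = 7: reject if the smaller rank sum is ≤ 2; size 2 × 3/128 = .047.
- n = 8: reject if ≤ 3; size 2 × 5/256 = .039.
- n = 15: reject if ≤ 25; size 2 × .02396 = .048.

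**4. Power** (200,000 simulated samples per setting). With a and b the power in the two independent arms: both significant = ab; neither = (1 − a)(1 − b); exactly one = a(1 − b) + b(1 − a). At dz .8, exactly one = .400 × .571 + .429 × .600 = .228 + .257 = .486.

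| dz | arm of 7 | arm of 8 | all 15 | both arms | neither | exactly one |
|---|---|---|---|---|---|---|
| .5 | 19% | 19% | 42% | 4% | 66% | 31% |
| .8 | 40% | 43% | 80% | 17% | 34% | 49% |
| 1.0 | 57% | 61% | 94% | 35% | 17% | 49% |
| 1.5 | 88% | 92% | >99% | 81% | 1% | 18% |

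(The last three columns may not sum to 100 because of rounding.)

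One-sided, the pattern is the same: 27% and 30% against 55% at dz .5, and 52% and 58% against 89% at dz .8. Exactly one arm is then significant in 41%, 50%, 40% and 9% of trials at dz .5, .8, 1.0 and 1.5.

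**5. Effect detectable with 80% power, two-sided.** dz of about 1.34 in the arm of 7, 1.26 in the arm of 8, and .80 on all 15.

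**6. Both ways of reading two per-arm results.** If success means both arms, power is 4%, 17% and 35% at dz .5, .8 and 1.0. If it means at least one arm, power is 34%, 66% and 83%, still below the 42%, 80% and 94% on all families. The false-positive risk is then 1 − (1 − .0469)(1 − .0391) = .084, against .048 for the single test.

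**The case against.** **The plan may mean what it tests.** The phrase *across groups* can mean pooled or in each of the groups, and the sentence before it expects a rise in both groups, which a per-arm test addresses. This stands: a reader might infer that the SAP contradicts the Measures section, and the wording does not support that. But the per-arm tests serve that reading poorly too, since both arms reach significance in only 4% of trials at dz .5 and 17% at .8.

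**The supplement may act on PRT delivery.** The Treatment paragraph says that mindfulness is applied to the PRT skills, and the treatment outline in Appendix B brings it into a coached parent-child session. Results by arm are therefore a defensible choice. This stands against removing per-arm results, and against extending the point to parent PRT fidelity, for which the SAP already plans a post-treatment arm comparison. It does not stand against adding an all-family test for utterances.

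**Low power is already admitted.** It is, and effect sizes are added. Those effect sizes are still per-arm figures on about 7 or 8 families, with no pooled estimate.

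**The inputs are assumed.** The split of 7 and 8, normality, dz, sidedness and the exact test are not in the documents, and the SAP itself anticipates non-normal data. The percentages are therefore illustrative. The gain from using all families holds one-sided as well as two-sided, provided that the arms change alike.

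**Conclusion.** The point holds for child utterances. The plan has no test of utterance change on all families. If both arms change alike, an all-family test has roughly twice the per-arm power at dz .5 to .8. Discordant arms are common, about 3 to 5 trials in 10 for dz .5 to 1.0, under the assumptions listed in the working.

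Some stronger conclusions that a reader might draw are not supported:
- *That discordance is the likely outcome.* At dz .5 the most probable two-sided result is that neither arm is significant (66%), and at dz 1.5 discordance falls to 18%.
- *That half the data are wasted.* Both arms are analysed, but each test uses only 7/15 or 8/15 of the families.
- *That an arm with five usable pairs could never reach .05.* This holds only for an exact two-sided test, where the smallest p is 2/32 = .0625. The SAP specifies neither feature, and one-sided the minimum is 1/32 = .031.
- *That pooling makes the trial adequately powered.* At the plan's .5, read as dz, 15 families give 42% two-sided or 55% one-sided, and 15 remains below the stated 27.

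**What to change.** In Statistical Analysis Plan, Group differences, for child utterances only:

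1. Prespecify as the main analysis of SLO change, for pre to post and for pre to follow-up, one exact signed-rank test on the change scores of all families. State in advance whether it is pooled or stratified by arm, whether it is one- or two-sided, and how zero and tied changes are handled.
2. Report the pooled median change with its interval.
3. Show each arm's median change beside it, and keep any per-arm tests as secondary.
4. State that one significant and one non-significant arm is not evidence of an arm difference.

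Leave parent fidelity, parenting stress, mindfulness and the other outcomes as planned.

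**Cost.** SAP wording only; no extra data. The pooled figure averages over the two supplements and loses power if only one arm changes, which is why the arm medians must appear with it.

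### Effect-size labels (.1/.3/.5) inform the judgement of treatment change at 7-8 pairs per arm with no interval, no definition of N and no bar on reading a label alone as change

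*Combined protocol and SAP*

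**What the plan says.** The Participants section sets the size of the trial: "A total of 15 caregivers and children will be randomly assigned to mPRT or pPRT groups". The allocation ratio is not stated.

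The Group differences part of the Statistical Analysis Plan gives the effect size in its Mann-Whitney paragraph: "To calculate effect size, the following formula will be" r = Z/√N. The labels follow: "interpretation of r values are as follows: .5 = large effect, .3 = medium effect, .1 = small effect".

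The next paragraph names the Wilcoxon signed-rank test, which "will be used to compare baseline and endpoint/follow-up scores for each group across variables of interest". It says that 27 are needed for a large effect and 648 for a small one, and continues: "Due to low power, effect sizes will also be calculated when determining change as a result of treatment".

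Four things are not stated: whether N in the paired setting is pairs or observations, any interval for r, how the label and the p-value combine, and what is concluded when they disagree.

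**The concern.** The reason given for bringing in r is low power, and the use given for it is judging change due to treatment. But r is Z divided by a constant. It has the same sampling error as the test and carries no further information. At 7-8 pairs that error is large: Z has standard deviation 1 when nothing has changed, so r has standard deviation 1/√7 = .38 or 1/√8 = .35 if N is pairs. The medium threshold of .3 lies inside one standard deviation of zero.

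Without an interval the reader cannot see this. A result described as a medium or large effect may be what chance commonly produces. Choosing pairs or observations for N also changes every r by √2 = 1.41, which can move a result from one label to another.

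**Working it through.** **Inputs.** 15 dyads (Participants); signed-rank test in each group, r = Z/√N, thresholds .3 and .5, and alpha .05 (Group differences). Assumed: an equal split (7 and 8 pairs), no dropout, no ties and no zero differences.

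**The plan's own figures.** 27 and 648 reproduce within tolerance at one-sided alpha .05 and 80% power, if the effect is read as a standardised paired mean difference of .5 or .1. A paired t-test needs 27 and 620; dividing by the signed-rank efficiency 3/π gives 28 and 649. By the plan's own count, 7-8 pairs is less than a third of what a large effect needs.

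**Null distribution of r.** With no true change, all 2^n sign patterns are equally likely. W is the smaller rank sum, with null mean n(n+1)/4 and variance n(n+1)(2n+1)/24.

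- n = 7: mean 14, variance 35, SD 5.916, 128 patterns.
- n = 8: mean 18, variance 51, SD 7.141, 256 patterns.

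Example, n = 7 and N = pairs: r of .3 needs Z of .3 × √7 = .794, a distance of .794 × 5.916 = 4.70 from 14, so W ≤ 9. Thirty patterns have a positive-rank sum of 9 or less. Both directions give 60/128 = 46.9%.

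| Pairs | N counts | r ≥ .3, either sign | same, continuity-corrected | r ≥ .5, either sign | same, continuity-corrected |
|---|---|---|---|---|---|
| 7 | pairs (7) | W ≤ 9: 60/128 = 46.9% | 37.5% | W ≤ 6: 28/128 = 21.9% | 15.6% |
| 8 | pairs (8) | W ≤ 11: 98/256 = 38.3% | 38.3% | W ≤ 7: 38/256 = 14.8% | 14.8% |
| 7 | observations (14) | W ≤ 7: 38/128 = 29.7% | 21.9% | W ≤ 2: 6/128 = 4.7% | 4.7% |
| 8 | observations (16) | W ≤ 9: 64/256 = 25.0% | 19.5% | W ≤ 3: 10/256 = 3.9% | 3.9% |

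The normal approximation 2(1 − Φ(.3√N)) agrees: 43% and 40% for pairs, 26% and 23% for observations. Favourable direction only: about 19-23% for pairs and 10-15% for observations.

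**What significance requires.** Exact two-sided p < .05 needs W ≤ 2 at n = 7 (p = .047) or W ≤ 3 at n = 8 (p = .039).

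- n = 7: Z = 12/5.916 = 2.03. r = 2.03/√7 = .77 for pairs, or 2.03/√14 = .54 for observations.
- n = 8: Z = 15/7.141 = 2.10. r = 2.10/√8 = .74 for pairs, or 2.10/√16 = .53 for observations.

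With N as pairs, a large label can therefore fall well short of significance. At n = 7, W = 5 gives r = (9/5.916)/√7 = .575, with exact p = 20/128 = .16.

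**Dropout.** With 6 pairs the chance of r ≥ .3 is 43.8% (pairs) or 31.2% (observations). With 5 pairs the smallest two-sided exact p is 2/32 = .0625, so no result can be significant.

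**The case against.** The strongest reply is that the labels have no decision role. A reader might infer that they stand in for significance, or that the plan will report a treatment effect whenever r passes .3. The text does not support that. The key sentence says effect sizes are calculated also, the signed-rank tests stay in the plan, alpha is stated, and no sentence lets a label override a p-value. This stands. The gap is that nothing prevents such a reading, in a sentence that gives low power as the reason for looking at r.

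Second, a rate of about 4 in 10 depends on N being pairs and on counting both directions. The formula appears in the Mann-Whitney paragraph, where N is naturally observations. Under that reading the rate is 2 to 3 in 10, and r ≥ .5 is exactly the event that the exact two-sided test rejects at 7 or 8 pairs, so a large label adds no false positives. This also stands, so both ranges are needed. The medium label stays exposed either way: 20% to 47% is about four to nine times 5%.

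Third, no change in either arm is not the expected case. Both arms receive the same PRT training, and the Child utterances section expects utterances to rise in both. The rates describe one test with no true change; they do not forecast how many of the trial's results will be wrong.

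Fourth, the plan has another error-based criterion: Reliable Change Indices with a 1.96 threshold for stress, mindfulness and positive feelings. These concern individuals and give no interval for the group-level r.

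Finally, fixed labels are a cited convention, and removing them would be a matter of preference. That is accepted, and the fix keeps them.

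**Conclusion.** The point holds in a limited form. The plan uses r and fixed labels alongside underpowered tests when judging change, with no interval, no definition of N for paired data and no statement that a label is not evidence in itself. With no true change at 7-8 pairs, a medium or larger label arises in about 38-47% of tests (N = pairs) or 20-30% (N = observations), and a large one in about 15-22% or 4-5%. Favourable direction only is half of each. With N as pairs, exact significance needs r of about .74-.77.

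These figures assume an equal split, no dropout and no ties or zero differences. The allocation ratio is not given, and ties are plausible on ratings and counts. The arithmetic for r is exact under these assumptions; how far the labels would influence the conclusions is not something the documents settle.

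A within-arm change, even a significant one, would not by itself show an effect of mPRT over pPRT, because both arms receive PRT training.

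**What to change.** In the Group differences section:

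1. Define N as the number of pairs for the signed-rank test and the total number of participants for the Mann-Whitney test. Pairs is the reading with the higher chance rates, so this step does not suffice without the next two.
2. For each outcome with a baseline, report the Hodges-Lehmann median change in each arm, and the between-arm shift in change, with exact 95% confidence intervals. Say what will be shown with 5 or fewer pairs in an arm, where a two-sided exact 95% signed-rank interval is not available (with 6 pairs the smallest p is 2/64 = .031, so it is).
3. Keep r and its labels as description only. State that a label alone is not evidence of change, and that the effect of mPRT versus pPRT is judged from the between-arm estimate and its interval.

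The cost is SAP wording and standard software output, with no extra data. The between-arm shift is a further estimate for outcomes where the section now names only within-arm tests. Some results will be described less favourably than their labels would suggest.
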